4.3. Criteria for Temporarily Delaying Vaccine Administration

The following conditions are temporary or self-limiting and a subject may be vaccinated once the condition(s) has/have resolved and no other exclusion criteria are met.

- Current febrile illness (oral temperature $\geq 100.4^{\circ}\text{F}$ [$\geq 38^{\circ}\text{C}$]) or other acute illness within 48 hours before investigational product administration.
- Any acute respiratory illness within 14 days before investigational product administration.

- Receipt of any inactivated vaccine within 14 days or any live vaccine within 28 days before or anticipated receipt of any vaccine within the 14 days after investigational product administration.
- Receipt of short-term (<14 days) systemic corticosteroids. Investigational product administration should be delayed until systemic corticosteroid use has been discontinued for at least 28 days. Inhaled/nebulized, intra-articular, intrabursal, or topical (epidural, skin, or eyes) corticosteroids are permitted.

4.4. Lifestyle Requirements

4.4.1. Contraception

All fertile male subjects who are, in the opinion of the investigator, sexually active and at risk for pregnancy with their partner(s) must agree to use a highly effective method of contraception consistently and correctly at least 28 days after the last dose of investigational product. The investigator or his or her designee, in consultation with the subject, will confirm that the subject has selected an appropriate method of contraception for the individual subject and his partner from the permitted list of contraception methods (see below) and will confirm that the subject has been instructed in its consistent and correct use. At time points indicated in the [Schedule of Activities](#), the investigator or designee will inform the subject of the need to use highly effective contraception consistently and correctly and document the conversation and the subject's affirmation in the subject's chart (subjects need to affirm their consistent and correct use of at least 1 of the selected methods of contraception). In addition, the investigator or designee will instruct the subject to call immediately if the selected contraception method is discontinued or if pregnancy is known or suspected in the subject's partner.

Highly effective methods of contraception are those that, alone or in combination, result in a failure rate of less than 1% per year when used consistently and correctly (ie, perfect use) and include the following:

- Established use of hormonal methods of contraception associated with inhibition of ovulation (eg, oral, inserted, injected, implanted, transdermal), provided the subject or male subject's female partner plans to remain on the same treatment throughout the entire study and has been using that hormonal contraceptive for an adequate period of time to ensure effectiveness. Correctly placed intrauterine device (IUD) or hormone-releasing intrauterine system (IUS).
- Male condom or female condom used WITH a separate spermicide product (ie, foam, gel, film, cream, or suppository). For countries where spermicide is not available or condom plus spermicide is not accepted as highly effective contraception, this option is not appropriate.
- Male sterilization with absence of sperm in the postvasectomy ejaculate.

- Bilateral tubal ligation/bilateral salpingectomy or bilateral tubal occlusive procedure (provided that occlusion has been confirmed in accordance with the device's label).

NOTE: Sexual abstinence, defined as completely and persistently refraining from all heterosexual intercourse (including during the entire period of risk associated with the study treatments) may obviate the need for contraception ONLY if this is the preferred and usual lifestyle of the subject.

4.5. Sponsor's Qualified Medical Personnel

The contact information for the sponsor's appropriately qualified medical personnel for the study is documented in the study contact list located in the supporting study documentation.

To facilitate access to appropriately qualified medical personnel on study-related medical questions or problems, subjects are provided with a contact card. The contact card contains, at a minimum, protocol and investigational product identifiers, subject study numbers, contact information for the investigator site, and contact details for a contact center in the event that the investigator site staff cannot be reached to provide advice on a medical question or problem originating from another healthcare professional not involved in the subject's participation in the study. The contact number can also be used by investigator staff if they are seeking advice on medical questions or problems; however, it should be used only in the event that the established communication pathways between the investigator site and the study team are not available. It is therefore intended to augment, but not replace, the established communication pathways between the investigator site and the study team for advice on medical questions or problems that may arise during the study. The contact number is not intended for use by the subject directly, and if a subject calls that number, he or she will be directed back to the investigator site.

5. INVESTIGATIONAL PRODUCTS

For the purposes of this study, and per International Council for Harmonisation (ICH) guidelines, investigational product is defined as a pharmaceutical form of an active ingredient or placebo being tested or used as a reference/comparator in a clinical trial, including a product with a marketing authorization when used or assembled (formulated or packaged) in a way different from the approved form, or when used for an unapproved indication, or when used to gain further information about an approved use (ICH E6 1.33).

For this study, the investigational products are RSV vaccine and placebo (saline control).

Commercially available SIIV will also be provided by the sponsor.

5.1. Allocation to Investigational Product

Allocation of subjects to vaccine groups will proceed through the use of an interactive response technology (IRT) system (interactive Web-based response [IWR]). Site staff will be required to enter or select information including but not limited to the user's identification (ID) and password, the protocol number, and the subject number.

The study-specific IRT reference manual will provide the contact information and further details on the use of the IRT system.

5.1.1. Blinding of Study Site Personnel

This is an observer-blinded study as the physical appearance of the RSV vaccine candidates and placebo may differ. SIV will be administered in an open-label fashion.

The subject, investigator, study coordinator, and other site staff will be blinded. At the study site, only the dispenser(s)/administrator(s) are unblinded.

Contact between the unblinded dispenser(s)/administrator(s) and study subjects should be kept to a minimum. The investigator, study coordinator, and any site staff other than the unblinded dispenser(s)/administrator(s) must not be allowed to know the investigational product assigned to any study subject and must not be allowed to see the investigational product.

5.1.2. Blinding of the Sponsor

The sponsor study team members will be blinded to the vaccine assigned/received by all subjects, from subject randomization up until 1 month after vaccination for the Primary Study Cohort - Stage 1 and from subject randomization up until 1 month after the second vaccination for the RSV Vaccine Month-0, Month-2 Cohort, when safety and immunogenicity data are available for analysis.

Laboratory personnel performing the immunologic assays will remain blinded to vaccine assigned/received throughout the study.

Certain sponsor personnel not directly involved in the conduct of the study will review safety data as defined in an IRC charter per Pfizer standard operating procedures (SOPs).

Unblinded sponsor personnel who are not part of the study team will be assigned to assess whether a stopping rule is triggered (see [Section 7.4](#)) for details) and for ongoing safety review.

Those study team members who are involved in ensuring that protocol requirements for investigational product handling, allocation, and administration are fulfilled at the site (eg, study manager; clinical research associates [CRAs]) will be unblinded for the duration of the study.

5.2. Breaking the Blind

At the initiation of the study, the investigator will be instructed on the method for breaking the blind for an individual subject. The method will be an electronic process. Blinding codes should be broken only in exceptional circumstances when knowledge of the actual treatment code is absolutely essential for further management of the subject. Investigators are encouraged to discuss with a member of the study team if they believe that unblinding is necessary. When the blinding code is broken, the reason must be fully documented and entered on the case report form (CRF).

5.3. Subject Compliance

All doses of investigational product will be administered by the appropriately designated study staff at the investigator site.

5.4. Investigational Product Supplies

5.4.1. Dosage Form(s) and Packaging

5.4.1.1. Respiratory Syncytial Virus Stabilized Prefusion F Subunit Vaccine

Each lyophilized vial of the RSV vaccine drug product is supplied as a mixture of equal

CCI

There are 3 different presentations of RSV drug product. The Al(OH)₃- and CpG/Al(OH)₃-containing formulations consist of 3 different dose levels of lyophilized RSV antigen (60 µg, 120 µg, and 240 µg). The RSV antigens without Al(OH)₃ or CpG/Al(OH)₃ will consist of a single dose level (240 µg). The lyophilized cake is reconstituted with one of 3 diluents: a sterile suspension of Al(OH)₃ in water for injection, a sterile suspension of CpG/Al(OH)₃, or sterile water for injection.

The fill volumes of the drug product vial and diluent vial are designed such that the intended vaccine dose is delivered in a 0.5-mL injection volume.

5.4.1.2. Seasonal Inactivated Influenza Vaccine

Commercially available high-dose (HD) trivalent SIIV (if available) or quadrivalent SIIV will be used in the Primary Study Cohort - Stage 1 and Stage 2.

Investigational sites will be notified which commercially available SIIV will be provided prior to the start of enrollment.

The World Health Organization may change its influenza vaccine reference strain recommendations from one northern or southern hemisphere influenza season to the next and may recommend more than 1 reference strain for each type A subtype or type B lineage; different national regulatory authorities may select different reference strains in a single season; and different SIIV manufacturers may choose different influenza vaccine strains that are antigenically like the selected reference strains. Therefore, the influenza vaccines that are available in different seasons and in different countries may have different strain compositions, and this study may necessarily include more than 1 SIIV formulation.

5.4.1.3. Placebo

The placebo will be a sterile normal saline solution for injection (0.9% sodium chloride injection, in a 0.5-mL dose).

Placebo will be provided by the sponsor to each study site. The placebo will be packaged within cartons labeled by Pfizer or its designee in accordance with current guidelines and applicable local and legal regulatory requirements.

5.4.2. Preparation and Dispensing

Investigational product preparation and dosing information will be provided in the investigational product (IP) manual.

The investigational product will be dispensed using an IRT investigational product management system.

5.5. Administration

Vaccine will be administered in the upper deltoid muscle by the **unblinded** administrator.

- Primary Study Cohort - Stage 1

Subjects will receive 2 injections at Visit 1 (Day 1) in accordance with the assigned randomized treatment; see [Table 6](#) below for administration guidance.

- Primary Study Cohort - Stage 2

Subjects will receive 2 injections at Visit 1 (Day 1) and 2 injections at Visit 5 (Month 12) in accordance with the assigned randomized treatment; see [Table 6](#) below for administration guidance.

- RSV Vaccine Month-0, Month-2 Cohort

Subjects will receive a single injection at Visit 1 (Month 0) and at Visit 3 (Month 2) in accordance with the assigned randomized treatment; see Table 6 below for administration guidance.

Standard vaccination practices must be observed, and vaccine must not be injected into blood vessels. Appropriate medication and other supportive measures for management of an acute hypersensitivity reaction should be available in accordance with local guidelines for standard immunization practices.

Administration of investigational products should be performed by an appropriately qualified, Good Clinical Practice (GCP)-trained, and vaccine-experienced member of the study staff

(eg, physician, nurse, physician's assistant, nurse practitioner, pharmacist, or medical assistant) as allowed by local, state, and institutional guidance.

Investigational product administration details will be recorded on the CRF.

Table 6. Location of Intramuscular Injection

Product Administered	Location of Injection
Primary Study Cohort - Stage 1 and Stage 2	
RSV+Al(OH) ₃ SIIV	Left deltoid muscle Right deltoid muscle
RSV+CpG/Al(OH) ₃ SIIV	Left deltoid muscle Right deltoid muscle
RSV SIIV	Left deltoid muscle Right deltoid muscle
Placebo SIIV	Left deltoid muscle Right deltoid muscle
RSV Vaccine Month-0, Month-2 Cohort	
RSV+CpG/Al(OH) ₃ or placebo	Left deltoid muscle

Abbreviations: Al(OH)₃ = aluminum hydroxide; RSV = respiratory syncytial virus vaccine; SIIV = seasonal inactivated influenza vaccine.

5.6. Investigational Product Storage

SIIV, investigational product, diluent, and placebo will be shipped at +2°C to +8°C to the study site after required regulatory and legal documents have been received by the sponsor. Upon receipt at the study site, SIIV, investigational product, diluent, and placebo should be immediately transferred to a +2°C to +8°C temperature-monitored refrigerator for storage.

The investigator or an approved representative, eg, pharmacist, will ensure that all investigational products and SIV are stored in a secured area with controlled access under required storage conditions and in accordance with applicable regulatory requirements.

Investigational products should be stored in their original containers and in accordance with the labels.

See the IP manual for storage conditions of the product once reconstituted.

Any storage conditions stated in the SRSD will be superseded by the storage conditions stated on the product label.

Site systems must be capable of measuring and documenting (for example, via a log), at a minimum, daily minimum and maximum temperatures for all site storage locations (as applicable, including frozen, refrigerated, and/or room-temperature products). This should be captured from the time of investigational product receipt throughout the study. Even for continuous-monitoring systems, a log or site procedure that ensures active evaluation for excursions should be available.

The intent is to ensure that the minimum and maximum temperature is checked each business day to confirm that no excursion occurred since the last evaluation and to provide the site with the capability to store or view the minimum/maximum temperature for all nonworking days upon return to normal operations. The operation of the temperature-monitoring device and storage unit (for example, refrigerator), as applicable, should be regularly inspected to ensure they are maintained in working order.

Any excursions from the product label storage conditions should be reported to Pfizer upon discovery. The site should actively pursue options for returning the product to the storage conditions described in the labeling, as soon as possible. Deviations from the storage requirements, including any actions taken, must be documented and reported to Pfizer.

Once an excursion is identified, the investigational product must be quarantined and not used until Pfizer provides permission to use the investigational product. It will not be considered a protocol deviation if Pfizer approves the use of the investigational product after the temperature excursion. Use of the investigational product prior to Pfizer approval will be considered a protocol deviation. Specific details regarding information the site should report for each excursion will be provided to the site.

5.7. Investigational Product Accountability

The investigator site must maintain adequate records documenting the receipt, use, loss, or other disposition of the investigational product supplies. All investigational products will be accounted for using a drug accountability form/record.

5.7.1. Destruction of Investigational Product Supplies

The sponsor or designee will provide guidance on the destruction of unused investigational product (eg, at the site). If destruction is authorized to take place at the investigator site, the investigator must ensure that the materials are destroyed in compliance with applicable environmental regulations, institutional policy, and any special instructions provided by Pfizer, and all destruction must be adequately documented.

5.8. Concomitant Treatment(s)

5.8.1. Prohibited Nonstudy Vaccines Prior to the Study

- Licensed or investigational RSV vaccines at any time.
- Receipt of any inactivated vaccine within 14 days or any live vaccine within 28 days before investigational product administration.
- Vaccination with any influenza vaccine within 6 months (182 days) before investigational product administration.

5.8.2. Prohibited Nonstudy Vaccines and Medications During the Study

- Nonstudy investigational vaccines, investigational drugs, or investigational medical devices are prohibited during the course of the study.
- Vaccination with any influenza vaccine within 6 months (182 days) before investigational product administration (applicable to Primary Study Cohort - Stage 2 subjects).
- Licensed or investigational RSV vaccines, blood/plasma products, or immunoglobulins are prohibited during the course of the study.
- Immunosuppressive therapy is prohibited during the study with the exception of inhaled/nebulized, intra-articular, intrabursal, or topical (epidural, skin, or eyes) corticosteroids, which are permitted.
- Unless considered medically necessary, no vaccines should be administered until at least 28 days after investigational product administration.
- Prophylactic antipyretics and other pain medication to prevent symptoms associated with investigational product administration are not permitted.

5.8.3. Permitted Nonstudy Vaccines and Medications During the Study

- Licensed influenza vaccine may be given during the study starting after the blood sample has been taken at the 1-month postvaccination visits (applicable to Primary Study Cohort - Stage 1 and Stage 2).

- For the RSV Vaccine Month-0, Month-2 Cohort, nonstudy licensed influenza vaccine may be given after Visit 3.
- If medically necessary (eg, pandemic), influenza vaccine may be given at any time.
- Inhaled/nebulized, intra-articular, intrabursal, or topical (epidural, skin, or eyes) corticosteroids are permitted.
- The use of antipyretics and other pain medication to treat symptoms associated with investigational product administration is permitted during subject participation in the study.
- Medication other than that described as prohibited in [Section 5.8.2](#) required for treatment of preexisting stable conditions is permitted.

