- The investigator or appropriately qualified designee reviews the e-diary data online following vaccination to evaluate subject compliance and as part of the ongoing safety review. Daily review is optimal during the active diary period.

6.3.2. RSV Vaccine Month-0, Month-2 Cohort, Visit 2A: 1-Week Follow-up Visit (6 to 8 Days After Visit 1) (*applies to subjects consenting to PBMC collection at PBMC collection sites only*)

- Review the subject's e-diary data.
- Record nonstudy vaccinations as described in [Section 5.8.4](#).
- Confirm understanding of and compliance with protocol requirements for contraception (male subjects only).
- Collect a blood sample of approximately 50 mL for cellular assays.
- Record AEs as described in [Section 8](#).
- Ask the subject to contact the site staff or investigator if a medically attended event (eg, doctor's visit, emergency room visit) or hospitalization occurs.
- Schedule an appointment for the subject to return for the next study visit.

- Complete the source documents.
- The investigator or an authorized designee completes the CRFs.

6.3.3. RSV Vaccine Month-0, Month-2 Cohort, Visit 2: 1-Month Follow-up Visit (28 to 35 Days After Visit 1) (*applies to all subjects*)

- Review the subject's e-diary data and collect the e-diary. Collect stop dates of any e-diary events ongoing on the last day that the e-diary was completed and record stop dates in the CRF if required.
- Record nonstudy vaccinations as described in [Section 5.8.4](#).
- Confirm understanding of and compliance with protocol requirements for contraception (male subjects only).
- Collect a blood sample of approximately 25 mL for antibody assessment.
- Collect a blood sample of approximately 50 mL for cellular assays (from consenting PBMC subjects at PBMC collection sites only).
- Record AEs as described in [Section 8](#).
- Complete the source documents.
- The investigator or an authorized designee completes the CRFs.
- Ask the subject to contact the site staff or investigator if a medically attended event (eg, doctor's visit, emergency room visit) or hospitalization occurs.

6.3.4. RSV Vaccine Month-0, Month-2 Cohort, Visit 3: Vaccination 2 Visit (54 to 66 Days After Visit 1) (*applies to all subjects*)

- Record nonstudy vaccinations as described in [Section 5.8.4](#).
- Ensure that the subject meets none of the temporary delay criteria as described in [Section 4.3](#).

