- Remind the subject to bring the completed e-diary to the next visit.

- Complete the source documents.
- The investigator or an authorized designee completes the CRFs and an unblinded dispenser/administrator updates the investigational product accountability records.
- The investigator or appropriately qualified designee reviews the e-diary data online following vaccination to evaluate subject compliance and as part of the ongoing safety review. Daily review is optimal during the active diary period.

6.3.5. RSV Vaccine Month-0, Month-2 Cohort, Visit 4A^a: 1-Week Post-Vaccination 2 Follow-up Visit (6 to 8 Days After Visit 3) (*applies to subjects consenting to PBMC collection at PBMC collection sites only*)

- Review the subject's e-diary data.
- Record nonstudy vaccinations as described in [Section 5.8.4](#).
- Confirm understanding of and compliance with protocol requirements for contraception (male subjects only).
- Collect a blood sample of approximately 50 mL for cellular assays.
- Record AEs as described in [Section 8](#).
- Ask the subject to contact the site staff or investigator if a medically attended event (eg, doctor's visit, emergency room visit) or hospitalization occurs.
- Schedule an appointment for the subject to return for the next study visit.
- Remind the subject to bring the completed e-diary to the next visit.
- Complete the source documents.
- The investigator or an authorized designee completes the CRFs.

6.3.6. RSV Vaccine Month-0, Month-2 Cohort, Visit 4: 1-Month Post-Vaccination 2 Follow-up Visit (28 to 35 Days After Visit 3) (*applies to all subjects*)

- Review the subject's e-diary data and collect the e-diary. Collect stop dates of any e-diary events ongoing on the last day that the e-diary was completed and record stop dates in the CRF if required.
- Record nonstudy vaccinations as described in [Section 5.8.4](#).
- Confirm understanding of and compliance with protocol requirements for contraception (male subjects only).
- Collect a blood sample of approximately 25 mL for antibody assessment.

- Collect a blood sample of approximately 50 mL for cellular assays (from consenting PBMC subjects at PBMC collection sites only).
- Record AEs as described in [Section 8](#).
- Complete the source documents.
- The investigator or an authorized designee completes the CRFs.
- Ask the subject to contact the site staff or investigator if a medically attended event (eg, doctor's visit, emergency room visit) or hospitalization occurs.

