4.3.2. Evaluable Immunogenicity Population

This evaluable immunogenicity population will include subjects who:

- Are eligible (have signed informed consent and met all inclusion/not met any exclusion criteria) and were randomized into the study;
- Have received both vaccinations at Months 0 and 2 as randomized;
- Have a Visit 4 (1 month after Vaccination 2) blood draw for assay testing within 27 to 42 days after Visit 3, inclusive (after vaccine administration) (note: the 27- to 42-day interval is calculated as the Visit 4 date minus the Visit 3 date);
- Have at least 1 valid and determinate assay result for the proposed analysis;
- Have no major protocol violation as determined by the study clinician.

Major protocol violations will be determined as described in [Section 4.1.2](#) by clinical review.

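### Protocol 5.8.3 lets the Month-0/Month-2 cohort have routine influenza vaccine after Visit 3 with no interval, which on its face is inconsistent with the 28-day bar on vaccines in 5.8.2

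*Protocol*

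**What the plan says.** Four rules bear on influenza vaccine after the second dose in the RSV Vaccine Month-0, Month-2 Cohort.

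- **Permission (Protocol 5.8.3).** "For the RSV Vaccine Month-0, Month-2 Cohort, nonstudy licensed influenza vaccine may be given after Visit 3". A separate bullet covers medical need: "If medically necessary (eg, pandemic), influenza vaccine may be given at any time". The first bullet is therefore about routine vaccination.
- **Bar (Protocol 5.8.2).** "Unless considered medically necessary, no vaccines should be administered until at least 28 days after investigational product administration". It is not limited to any cohort.
- **Check at Visit 3 (Protocol 6.3.4 and 4.3).** Before the second dose, site staff must do the following: "Ensure that the subject meets none of the temporary delay criteria as described in" Section 4.3. Looking forward, the relevant criterion there is "anticipated receipt of any vaccine within the 14 days after investigational product administration". It delays the study dose; it does not forbid the outside vaccine.
- **Evaluability (SAP 4.3.2, referring to 4.1.2).** The Visit 4 sample must be a "blood draw for assay testing within 27 to 42 days after Visit 3, inclusive". Major violations are settled by clinical review, and receipt of a prohibited vaccine that might affect immune response is one of the examples given.

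Protocol 6.3.4 confirms that Visit 3 is the second-dose visit, and 6.3.6 puts Visit 4 at 28 to 35 days after it. Protocol 8.1.4 collects adverse events in this cohort through Visit 4.

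**The concern.** The cohort-specific sentence is the one a site will look up when a participant asks about influenza vaccine, and it names a visit, not an interval. Taken alone, it allows vaccination from the day of the second dose. The general rule one section earlier forbids that for 28 days.

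Two things are at stake. First, an influenza vaccine given between Visit 3 and Visit 4 sits inside the period used to describe the second dose: adverse events to Visit 4, and the 1-month post-Vaccination 2 titers and fold rises, including the fold rise from 1 month after Vaccination 1 to 1 month after Vaccination 2 (SAP 3.2.1, item 3c). The cohort was set up without concomitant influenza vaccine, and SAP 7.2 says the interim results help choose the dosing schedule. Second, when the medical monitor reviews violations, it is unclear whether such a vaccine counts as prohibited at all.

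**Working it through.** The plan states no figure on this point. The check compares the rules and counts days, with day *n* meaning *n* days after Visit 3.

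**Inputs**
- Visit 3: 54 to 66 days after Visit 1 (Protocol 6.3.4).
- Visit 4: days 28 to 35 (Protocol 6.3.6). SAP 4.3.2 accepts draws on days 27 to 42.
- Bar on vaccines: 28 days (Protocol 5.8.2).
- Forward check: 14 days (Protocol 4.3).
- Diary: 14 days with the vaccination day as Day 1 (Protocol 6.3.4), so days 0 to 13 here.

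**Step 1: days on which the texts disagree.** 5.8.3 alone opens on day 0; 5.8.2 opens on day 28. They disagree on days 0 to 27.

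**Step 2: what the 4.3 check removes.** A planned dose on days 0 to 14 should cause Vaccination 2 to be delayed. A dose planned for days 15 to 27 passes the check and still breaches 5.8.2. A dose not anticipated at Visit 3 is not caught on any of days 0 to 27. For planned doses the check covers the whole diary period, because 14 is later than 13.

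**Step 3: gap between the earliest dose and the Visit 4 draw** (gap = draw day − earliest dose day, with 0 as the floor).

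| Rules applied | Earliest day | Protocol draw, days 28–35 | SAP draw, days 27–42 |
|---|---|---|---|
| 5.8.3 alone | 0 | 28 to 35 | 27 to 42 |
| 5.8.3 with the 4.3 check, planned dose | 15 | 13 to 20 | 12 to 27 |
| 5.8.3 with 5.8.2 | 28 | 0 to 7 | 0 to 14 |

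The first row is an upper bound and applies only to doses not anticipated at Visit 3. Every day from 0 to 27 precedes a draw made in the protocol window.

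**Step 4: position relative to Visit 1.**
- Earliest routine influenza vaccine under 5.8.3 alone: days 54 to 66.
- Under 5.8.2: 54 + 28 = 82 to 66 + 28 = 94.
- Visit 4 in the protocol window: 54 + 28 = 82 to 66 + 35 = 101.

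**Step 5: effect of the correction.** With 5.8.3 set at no earlier than day 28, the days of disagreement fall from days 0 to 27 to none.

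**The case against.** The strongest reply is that there is no true contradiction. Under 5.8.2 alone, influenza vaccine could be given between the two study doses, from day 28 after the first. The 5.8.3 sentence moves it to after Visit 3, and 5.8.2 then supplies the interval. Each rule has a job on that reading, and nothing in 5.8.3 sets 5.8.2 aside. This stands as far as it goes: a reader might infer that the two sections cannot be reconciled, and the documents do not support that. But the text states neither the cumulative reading nor a deliberate exception, and the two give different earliest days (28 against the day of Visit 3). Either intention needs a wording change.

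Other replies also stand in part:

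- **Evaluability.** One might infer that the choice of rule decides whether a subject stays in the evaluable population. It does not. SAP 4.1.2 leaves that to the medical monitor, who must judge a material effect on the immunogenicity assessment, before any immunogenicity analysis. A dose on day 20 need not exclude anyone under either rule. What is left is uncertainty over one input to that judgment.
- **The long gaps.** One might take 35 or 42 days as typical. The 4.3 check should prevent this for planned vaccine and should keep planned vaccine out of the reactogenicity diary.
- **Harm.** The documents give neither influenza vaccine uptake nor any effect of it on RSV titer. The placebo arm has the same permission, so a nonspecific shift could show there. The cohort enrolls before the influenza season, so few doses may fall before Visit 4.
- **The Stage 1 and Stage 2 rule.** In those stages influenza vaccine waits for the 1-month sample. That is not a direct benchmark, because they include study influenza vaccine and influenza endpoints that this cohort lacks.

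**Conclusion.** The point holds as an inconsistency in wording that can change what sites do. Routine influenza vaccine on days 0 to 27 after Vaccination 2 is allowed by 5.8.3 read alone and barred by 5.8.2. The 4.3 check leaves open planned doses on days 15 to 27 and unplanned doses on days 0 to 27.

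Severity is minor. SAP 4.3.3 describes this cohort as entirely exploratory. The Stage 1 primary and secondary endpoints are unaffected, as is the 1-month post-Vaccination 1 comparison of RSV response with and without influenza vaccine. A reader might infer that the post-Vaccination 2 titers are biased; the documents give no basis for a direction or a size, and none is claimed. The conclusion rests on the text and visit windows alone, with the first 5.8.3 bullet taken to cover routine vaccination because medical need has its own bullet.

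**What to change.** **Protocol.** Amend the 5.8.3 bullet so that, for this cohort, routine influenza vaccine may be given no earlier than 28 days after Vaccination 2, in line with 5.8.2. Keep the medical-necessity exception.

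**SAP.** Report, per arm, the number of subjects given influenza vaccine after Visit 3 and before the Visit 4 draw. The dates are already collected (Protocol 5.8.4). The nonstudy vaccine output in SAP 6.5.2.2 is optional and not tied to this interval. The documents do not give the cohort's visit dates; if Visit 4 has passed for all subjects, only this step applies.

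**Cost.** One protocol line and one count. Adults aged 65 to 85 would get elective influenza vaccine later than under 5.8.3 read alone (days 82 to 94 after Visit 1 against 54 to 66), but no later than 5.8.2 already requires.

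**Optional.** Waiting for an in-window Visit 4 sample adds at most 35 − 28 = 7 days. A supportive 1-month post-Vaccination 2 summary without the flagged subjects is also possible. Its log-scale 95% CI half-width is proportional to t(0.975, n−1)/√n, so dropping 1, 3 or 6 of an assumed 31 widens it by about 2%, 6% or 13% at the same SD (ratios 1.018, 1.057 and 1.125). Neither is needed to resolve the inconsistency.
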